6.3 Pharmacodynamic Analyses Set

The PD analysis set will contain all study subjects who receive at least one dose of AMG 529 or placebo and for whom at least 1 PD parameter has a baseline and at least 1 post baseline measurement available.

7. Planned Analyses

The study will have dose level review meetings (DLRM) after each cohort. The DLRM members are responsible for dose level decisions. The key objectives of the DLRM are to review data, monitor safety, and make dose change decisions. The DLRM members will consist of the principal investigator or designee, Amgen Medical Monitor, Amgen Global Safety Officer or designee, Amgen Clinical Research Study Manager or designee, and a Biostatistics representative or designee. Additional members may be added as needed (eg, PK scientist). DLRMs will be conducted blinded to the PI and the Clinical Research Manager or their designees.

7.1 Interim Analysis and Early Stopping Guidelines

No interim analysis is planned for this study. However study will have Dose Level Review Meetings (DLRMs) after each cohort.

7.1.1 Dose-cohort Study Escalations and Stopping Rules

Dose-Cohort Study Escalation

The DLRM members are responsible for dosing decisions, which may include escalation to the next planned dose, escalation to an intermediate dose (a dose lower than the next planned dose), de-escalation to a lower dose; continuation, delay, or termination of dosing; or repetition or expansion of a cohort.

Study data, including demographics, investigational product administration, medical history, concomitant medications, adverse events (including serious adverse events), electrocardiograms, vital signs, and safety laboratory results will be reviewed. If available, emerging PK and PD data may also be reviewed in a manner that does not unblind individual treatment assignments.

Dose Stopping and Review

Determination of the severity of adverse events will be as follows: grade 1 = mild (eg, asymptomatic or mild symptoms, clinical or diagnostic observations only, intervention not indicated, or does not interfere with activity); grade 2 = moderate (eg, minimal intervention indicated or interferes with activity); grade 3 = severe (eg, medically significant but not immediately life-threatening, prevents daily activity, or requires treatment); grade 4 = life-threatening (ie, refers to an event in which the subject was, in the view of the investigator, at risk of death at the time of the event); and grade 5 = fatal. Dosing will be stopped or modified by the DLRM members if suspected adverse drug reactions and/or changes in safety data (including but not limited to

vital signs, electrocardiogram (ECG), or clinical laboratory results) are observed and these changes pose a significant health risk. The unblinded Amgen Medical Monitor will review data in an unblinded manner on an ongoing basis, and may suspend dosing and convene a DLRM at any time based on emerging safety data. In addition, dose escalation will be stopped or modified as shown in table below.

Clinically or medically significant suspected adverse drug reactions, and serious adverse events considered to be related to study procedures will be followed until resolved or considered stable.

Scenario	Action
Any occurrence of a Grade 2 suspected adverse drug reaction in 2 or more subjects in the same cohort	
• Stop dosing additional subjects and convene DLRM (if event occurs outside of the regularly scheduled DLRM)• Review adverse event and all relevant safety data for evidence of relationship to treatment and clinical or medical significance• Consider unblinding as appropriate¹• Upon unanimous decision by the DLRM members, one of the following decisions may be made:
- stop enrollment of the cohort (if applicable)- resume enrollment of the cohort as planned- resume enrollment of the cohort at a lower dose- expand the cohort at same dose- add a lower dose cohort to the study- escalate to an intermediate dose (a dose lower than the next planned dose)- escalate to the next planned dose

Scenario	Action
Any occurrence of a Grade 3 or greater suspected adverse drug reaction	
 • Stop dosing additional subjects and convene DLRM (if event occurs outside of the regularly scheduled DLRM) • Review adverse event and all relevant safety data for evidence of relationship to treatment and clinical or medical significance • Consider unblinding as appropriate¹ • If the adverse event is determined by unanimous decision of the DLRM members to be related to study drug and clinically or medically significant, no further doses should be administered at this dose and no dose escalation should proceed. Enrollment of the study may continue at a lower dose or a lower dose cohort may be added to the study. • Otherwise, upon unanimous decision of the DLRM members, one of the following decisions may be made: 
 - resume enrollment of the cohort as planned - resume enrollment of the cohort at a lower dose - expand the cohort at the same dose - add a lower dose cohort to the study - escalate to an intermediate dose (a dose lower than the next planned dose) - escalate to the next planned dose

¹ The Amgen Medical Monitor will be unblinded to treatment assignment throughout the duration of the study.

For other DLRM members, a subject's treatment assignment should only be unblinded when knowledge of the treatment is essential for the further management of the subject, or may impact the safety of subjects currently enrolled, or subjects in subsequent cohorts.

7.2 Primary Analysis

The primary analysis will occur after the database lock following last subject last visit.

7.3 Final Analysis

The primary analysis will be the final analysis.

8. Data Screening and Acceptance

8.1 General Principles

The objective of the data screening is to assess the quantity, quality, and statistical characteristics of the data relative to the requirements of the planned analyses.

8.2 Data Handling and Electronic Transfer of Data

The Amgen Global Study Operations-Data Management (GSO-DM) department will provide all data to be used in the planned analyses. This study will use the [rave](#) database. The database will be subject to edit checks outlined in the Clinical Data Management Plan (DMP). See details of this section in the DMP.

8.3 Handling of Missing and Incomplete Data

The following imputation of missing values will be done:

- Incomplete adverse event and concomitant medication dates will be imputed as per [Appendix A](#). If imputed dates are used, then they will be identified as such in the final study report.
- Laboratory measurements that are below the quantification limits will be considered equal to the lower limit of quantification for all analyses unless explicitly noted otherwise.
- Biomarker data that are below the quantification limits will be considered equal to half of the lower limit of quantification for all analyses unless specified otherwise.
- PK concentrations that are below the quantification limits will be set to zero when engaging non-compartmental model to compute PK parameters.

8.4 Detection of Bias

Lack of protocol compliance and the potential for biased statistical analyses will be examined by assessing the incidence of important protocol deviations. The clinical study team will identify and document the criteria for important protocol deviations following Amgen SOP.

8.5 Outliers

Details of detecting outliers can be found in the DMP or other data management document. In addition, outliers may be identified via the use of descriptive statistics. All confirmed outlier data will be included in the analyses presented in this statistical analysis plan unless there is sufficient scientific justification to exclude them.

Pharmacokinetic (PK) [serum](#) concentration data will be evaluated for outliers by visual inspection, and decisions to re-assay individual samples will be made in accordance with standard pharmacokinetic evaluation practice.

8.6 Distributional Characteristics

Where appropriate, the assumptions underlying the proposed statistical methodologies will be assessed. Data distribution will be explored, if required, data transformations or alternative non-parametric methods of analyses will be utilized.

8.7 Validation of Statistical Analyses

Programs will be developed and maintained, and output will be verified in accordance with current risk-based quality control procedures.

Tables, figures, and listings will be produced with validated standard macro programs where standard macros can produce the specified outputs.

The production environment for statistical analyses consists of Amgen-supported versions of statistical analysis software; for example, the SAS System version 9.4 or later.

9. Statistical Methods of Analysis

9.1 General Considerations

Descriptive statistics will be provided for selected demographics, safety, PK, and PD data. Data for subjects receiving placebo will be combined across all cohorts, except for adverse events where the combined SC cohorts will be summarized separately from the IV cohort. Descriptive statistics on continuous measurements will include means, medians, standard deviations, and ranges, while categorical data will be summarized using frequency counts and percentages. Data will be summarized by treatment group and at each time point when samples are collected. The number and percent of subjects reporting any treatment-emergent adverse events will be tabulated by system organ class and preferred term and will be further classified by relationship to treatment.

9.2 Subject Accountability

The number and percent of subjects who were enrolled, randomized, received investigational product, completed investigational product, discontinued from investigational product (including reasons for discontinuing), completed study, discontinued the study (including reasons for discontinuing) will be summarized by treatment group.

Key study dates for the first subject enrolled, last subject enrolled, and last subject's end of study will be presented. A subject listing and summary noting inclusion in each analysis subset will be reviewed for all subjects enrolled. A subject listing noting reason for discontinuation of treatment and reason for discontinuing the study will be reviewed.

A subject listing will be provided for randomization information, randomized treatment and actual treatments.

9.3 Important Protocol Deviations

Important Protocol Deviations (IPDs) categories are defined by the study team before the first subject's visit and updated during the IPD reviews throughout the study prior to database lock. If a snapshot is being taken during the study rather than a database lock at the end of the study, categories should be updated during the IPD reviews throughout the study prior to database lock. These definitions of IPD categories, sub-category codes, and descriptions will be used during the course of the study. Eligibility deviations are defined in the protocol. The final IPD list is used to produce the list of subjects with IPDs. In addition, a separate listing of all inclusion and exclusion deviations will be provided.

9.4 Demographic and Baseline Characteristics

Demographic (ie, age, age groups [< 65 , ≥ 65 and ≥ 75], sex, race, ethnicity) and baseline characteristics (height, weight, body mass index) will be summarized by cohort and overall using descriptive statistics. If multiple races have been reported for a subject, the subject will be categorized as multiple race as well as by the combination of race.

9.5 Efficacy Analyses

Not applicable.

9.6 Safety Analyses

9.6.1 Analyses of Primary Safety Endpoint(s)

9.6.2 Adverse Events and Disease-related Events

All subjects who receive a dose of AMG 529 or placebo will be included in the safety analyses. Subject incidence of all treatment-emergent adverse events will be tabulated by system organ class and preferred term according to the medical dictionary for regulatory activities terminology. Tables of adverse events, fatal adverse events, and serious adverse events will also be provided if observed.

The Medical Dictionary for Regulatory Activities (MedDRA) version 19.0 or later will be used to code all adverse events to a system organ class and a preferred term. The subject incidence of adverse events by treatment group will be summarized for all treatment emergent, serious treatment emergent, treatment related, serious treatment related, those leading to withdrawal of investigational product, severe, life threatening and fatal adverse events.

The severity of each adverse event will be graded using protocol defined criteria. Subject incidence of treatment emergent events and treatment related treatment emergent events will further be summarized by worst severity grade. Subject incidence of all treatment emergent, serious treatment emergent, treatment emergent events leading to withdrawal of investigational product, and treatment emergent fatal adverse events will further be tabulated by system organ class and preferred term in descending order of frequency.

The above adverse event tables will not be created if two or fewer subjects in the study experience the adverse event. Narratives of any on-study deaths, serious treatment-emergent adverse events, including early withdrawals due to adverse events, also will be provided should they occur.

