**Table 3. Cohort Dose Stopping Rules**

Scenario	Action
Any occurrence of a Grade 2 suspected adverse drug reaction in 2 or more subjects in the same cohort	

• Stop dosing additional subjects and convene DLRM (if event occurs outside of the regularly scheduled DLRM)

• Review adverse event and all relevant safety data for evidence of relationship to treatment and clinical or medical significance

• Consider unblinding as appropriate

• Upon unanimous decision by the DLRM members, one of the following decisions may be made:

○ stop enrollment of the cohort (if applicable)

○ resume enrollment of the cohort as planned

○ resume enrollment of the cohort at a lower dose

○ expand the cohort at the same dose

○ add a lower dose cohort to the study

○ escalate to an intermediate dose (a dose lower than the next planned dose)

○ escalate to the next planned dose

Page 1 of 2

Footnotes defined on next page of the table

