##### **10.5.2 Primary Endpoints**

###### **10.5.2.1 Safety Endpoints**

###### **10.5.2.1.1 Adverse Events**

All subjects who receive a dose of AMG 529 or placebo will be included in the safety analyses. Subject incidence of all treatment-emergent adverse events will be tabulated

by system organ class and preferred term according to the medical dictionary for regulatory activities (MedDRA) terminology. Tables of adverse events, fatal adverse events, and serious adverse events will also be provided if observed.

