3.1 Study Design

This is a randomized, double-blind, placebo-controlled, ascending single-dose study in healthy subjects, which will be conducted at 1 to 3 sites in the United States.

Approximately 48 subjects will enroll in 1 of 6 dose cohorts (8 per cohort).

For cohorts 1, 2, 3, 4, and 5, eight (8) subjects will be randomized to receive AMG 529 or placebo SC in a 3:1 ratio at dose levels of 21, 70, 210, 420, and 700 mg, respectively.

In cohort 6, eight (8) subjects will receive AMG 529 or placebo IV in a 3:1 ratio at a dose level of 70 mg. The planned doses of AMG 529 are shown below:

Planned Treatment by Cohort

Cohort	Dose/Route	No. of Subjects		
		AMG 529	Placebo	Total
1	21 mg SC	6	2	8
2	70 mg SC	6	2	8
3	210 mg SC	6	2	8
4	420 mg SC	6	2	8
5	700 mg SC	6	2	8
6	70 mg IV	6	2	8

For all cohorts, the first 2 subjects (sentinel pair) will be randomized such that 1 subject will receive AMG 529 and 1 subject will receive placebo, and observed for at least 24 hours before the remaining subjects in the cohort are dosed, provided there are no safety or tolerability concerns as assessed by the principal investigator. Escalation to a higher dose cohort will only proceed when the previous dose regimen has been found to be safe and reasonably tolerated based on available safety and laboratory data through study day 15 for all subjects and upon unanimous decision at the Dose Level Review Meeting (DLRM). Enrollment can be initiated in cohort 5 and cohort 6 after the dose regimen in cohort 4 has been found to be safe and well tolerated. Cohort 6 will start enrollment after the completion of cohort 5 enrollment.

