3.2 Sample Size

The sample size is based on practical considerations. Approximately 48 healthy subjects will enroll to participate in cohorts 1 through 6 of this study. With 6 subjects receiving AMG 529 in a cohort there is a 74% chance of detecting an adverse event with a true incidence of 20%. With 36 subjects receiving AMG 529 there is an 84% chance of detecting an adverse event with a true incidence of 5%.

4. Covariates and Subgroups

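### SAP 9.6.2 withholds adverse event tables when two or fewer subjects in the study are affected, contradicting the commitment to tabulate whatever is observed, and does not say whether the cut-off is per table or per event

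*SAP*

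**What the plan says.** Subject incidence of treatment-emergent adverse events is a primary endpoint (Protocol 10.1.1.1; SAP 2.1). The plan makes three statements about tabulating it.

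- Protocol 10.5.2.1.1: "Tables of adverse events, fatal adverse events, and serious adverse events will also be provided if observed". SAP 9.6.2 repeats this sentence.
- Protocol 10.5.1 and SAP 9.1 commit, without any minimum count, to tabulating treatment-emergent events by system organ class and preferred term, and by relationship to treatment.
- SAP 9.6.2, after naming its summaries (all treatment-emergent, serious, related, serious related, leading to withdrawal, severe, life-threatening, fatal, and by worst grade), adds: "The above adverse event tables will not be created if two or fewer subjects in the study experience the adverse event".

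The protocol contains no such threshold, and SAP Section 10 says the protocol-specified analyses are unchanged. SAP 9.6.2 provides narratives for deaths, serious events and withdrawals due to adverse events. It names no adverse event listing, although the SAP does specify listings for randomization (9.2), eligibility deviations (9.3), urinalysis (9.6.3), antibodies (9.6.6) and lot numbers (9.6.7).

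**The concern.** A single affected subject satisfies the first two statements; the third asks for three. A programmer following the last sentence of 9.6.2 would omit output that the protocol promises for a primary endpoint, and no change would be on record.

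The sentence also has two readings. It speaks of tables not being created, which suggests dropping a sparse table. It then counts subjects with the adverse event, in the singular, which suggests dropping a sparse term. If this is not settled before database lock, what is shown for one- and two-subject events depends on a choice made with the data in view.

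Counts of one or two matter here because each dose has six active subjects. The plan's own detection figures also rest on seeing at least one affected subject.

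**Working it through.** **Inputs.** 48 subjects: 6 cohorts of 6 active and 2 placebo, so 36 active and 12 placebo (SAP 3.1). Detection figures: 74% for n = 6 at 20% incidence, 84% for n = 36 at 5% (SAP 3.2). Table threshold: at least 3 subjects in the study (SAP 9.6.2). Subjects are treated as independent with a common incidence. Incidences other than 20% and 5% from SAP 3.2 are assumptions, as are all background rates.

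**Step 1: reproduce the plan's figures.** P(at least 1) = 1 − (1 − p)^n.
- n = 6, p = 0.20: 1 − 0.8^6 = 0.738 (stated 74%).
- n = 36, p = 0.05: 1 − 0.95^36 = 0.842 (stated 84%).

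Both reproduce only if detection means at least one subject. Requiring at least two gives 0.345 and 0.543.

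**Step 2: per-table reading.** The count is of subjects with any event in the table's category, among 48. P(at least 3) = 1 − P(0) − P(1) − P(2).
- Serious events at an assumed 2%: P(at least 1) = 1 − 0.98^48 = 0.621. P(0), P(1) and P(2) are 0.379, 0.371 and 0.178, so P(at least 3) = 0.071.

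| Assumed category incidence | P(at least 1 of 48) | P(table created) |
|---|---|---|
| 1% | 38% | 1.2% |
| 2% | 62% | 7% |
| 5% | 91% | 43% |

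The table of all treatment-emergent events would be created with probability 87% if 10% of subjects have any event, and above 99% at 20% or more.

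**Step 3: per-event reading, no cases outside the stated group.**
- n = 6, p = 0.20: P(0), P(1), P(2) = 0.262, 0.393, 0.246, so P(at least 3) = 0.099. P(1 or 2) = 0.639, and 0.639/0.738 = 87% of detected cases would be untabulated.
- n = 36, p = 0.05: P(0), P(1), P(2) = 0.158, 0.299, 0.275, so P(at least 3) = 0.268. P(1 or 2) = 0.574, and 0.574/0.842 = 68% would be untabulated.

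**Step 4: allow cases elsewhere.** The threshold counts the whole study, so background cases help an event reach three. With A cases in the cohort's 6 active subjects and C in the other 42, the event is untabulated with probability P(A=1)·P(C≤1) + P(A=2)·P(C=0).

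| Assumed background in other 42 | P(occurs in cohort, no table) | Share of the 0.738 detected |
|---|---|---|
| 0% | 0.639 | 87% |
| 1% | 0.528 | 72% |
| 2% | 0.418 | 57% |
| 5% | 0.175 | 24% |

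For the 36-subject case, if placebo also has 5%, the untabulated share falls from 68% to 0.412/0.842 = 49%.

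**The case against.** The strongest defence is that the sentence concerns tables, not rows. The tables in 9.6.2 are category tables that each hold many terms; skipping a nearly empty one is a natural reading, and a row filter is nowhere described. On that reading an event in one or two subjects would still appear in the all-event table and count in the worst-grade summary, provided three subjects have any treatment-emergent event. This stands. It confines the Step 3 and Step 4 figures to the per-event reading. It does not remove the contradiction: the fatal and serious tables promised in the protocol would still need three subjects each, and the serious-event figures in Step 2 arise on this very reading.

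A reader might infer more than the documents support.

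- *That a non-serious severe or related event in one or two subjects would appear in no planned output.* This is open only on the per-event reading. Per table, it would normally be shown in the overall tables. Deaths, serious events and withdrawals due to adverse events have narratives on either reading.
- *That the trial was sized to see such counts, so its sample-size basis is breached.* SAP 3.2 says "The sample size is based on practical considerations". The 74% and 84% are chances that an event occurs in at least one subject, not commitments about table layout.
- *That safety oversight is weakened, because stopping triggers fall below the threshold.* Protocol Table 3 does act on small counts, for example "Any occurrence of a Grade 2 suspected adverse drug reaction in 2 or more subjects in the same cohort". But those rules run on ongoing unblinded monitoring and on dose level review of the adverse event data (Protocol 6.2.1.2.1 and 6.2.1.2.2), not on end-of-study tables.
- *That events at an SC dose would be set against 12 placebo subjects.* For adverse events, SC and IV placebo are summarized separately (Protocol 10.5.1; SAP 9.1), giving 5 × 2 = 10 SC and 2 IV.

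The protocol's condition of being observed names the adverse, fatal and serious event tables, and 10.5.1 adds relationship. The severe, life-threatening, withdrawal and worst-grade summaries are SAP additions, so for those the problem is the undefined threshold rather than a broken protocol commitment.

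**Conclusion.** The contradiction is real on either reading and is undeclared. It affects the final reporting of a primary endpoint.

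Its size depends on the reading. Per table, the loss falls on the sparse subset tables: 62% chance of occurrence against 7% chance of a table for serious events, resting on an assumed 2% incidence. Per event, the chance of reaching a table is 9.9% where the plan states 74%, and 26.8% where it states 84%. Those two figures assume no cases outside the stated group; background cases lessen the loss, to 24% of detected one-cohort events at an assumed 5% background. On the per-event reading, non-serious severe or related events also have no guaranteed substitute, since no adverse event listing is named.

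**What to change.** Delete the sentence from SAP 9.6.2, so that the adverse event tables are produced whenever at least one event is observed, with SC and IV placebo shown separately as SAP 9.1 requires. Add a subject-level listing of all treatment-emergent events giving treatment and dose, onset day, grade and relatedness.

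If the sponsor wants to keep a threshold for sparse subset tables, the SAP should state that it applies per table, replace each omitted table with that listing, and declare the rule in Section 10.

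Either change should be made before database lock. The cost is a short SAP edit, a few sparse tables and one listing; no additional data are collected, because Protocol 9.2.1.1 already has the investigator record onset, severity and relatedness.
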